8.5.6.1 Retreatment Day 1 Visit

The following procedures will be conducted at the Retreatment Day 1 Visit:

- Confirmation of recurrent, acute AMR, as shown by biopsy.
- Physical examination.
- Vital signs.
- Blood draws:
 - Creatinine.
 - Serum pregnancy test (for female subjects of childbearing potential).
 - Retention sample for viral serology.

NOTE: All blood draws should be completed before administration of C1-INH and IVIg.

- Subcutaneous administration of blinded investigational product (C1-INH [60 IU/kg] or placebo, dose rounded to the lowest 1 mL).
- Investigational product dispense, if applicable.
- IVIg may begin if DSA is ≥ 2000 MFI (2 grams/kg total dose; the dose must be administered over a minimum period of at least 2 days, and may be administered over a period of up to 5 days).

- Adverse events.
- Concomitant therapies.
- Schedule next visit.

8.5.6.2 Retreatment Day 7 Visit

The following procedures will be conducted at the Retreatment Day 7 Visit:

- Blood draws:
 - Creatinine.
- NOTE: The blood draw should be completed before administration of C1-INH.
- Subcutaneous administration of blinded investigational product (C1-INH [60 IU/kg] or placebo, dose rounded to the lowest 1 mL).
- Investigational product dispense, if applicable.
- Investigational product vial return, if applicable.
- Adverse events.
- Concomitant therapies.
- Schedule next visit.

8.5.6.3 Retreatment Week 4 and Week 8 Visits

The following procedures will be conducted at the Retreatment Week 4 and Week 8 Visits:

- Urine or serum pregnancy test (for female subjects of childbearing potential).
- Blood draws:
 - Creatinine.
- NOTE: The blood draw should be completed before administration of C1-INH and IVIg.
- Subcutaneous administration of blinded investigational product (C1-INH [60 IU/kg] or placebo, dose rounded to the lowest 1 mL).
- Investigational product dispense, if applicable.
- Investigational product vial return, if applicable.
- IVIg may begin if DSA is \geq 2000 MFI (2 grams/kg total dose; the dose must be administered over a minimum period of at least 2 days, and may be administered over a period of up to 5 days).
- Adverse events.

- Concomitant therapies.
- Schedule next visit.

8.5.6.4 Retreatment Week 12 Visit

The following procedures will be conducted at the Retreatment Week 12 Visit:

- Physical examination.
- Vital signs.
- Urine or serum pregnancy test (for female subjects of childbearing potential).
- Blood draws:
 - Creatinine.

NOTE: The blood draw should be completed before administration of C1-INH and IVIg.

- Subcutaneous administration of blinded investigational product (C1-INH [60 IU/kg] or placebo, dose rounded to the lowest 1 mL).
- Investigational product dispense, if applicable.
- Investigational product vial return, if applicable.
- IVIg may begin if DSA is \geq 2000 MFI (2 grams/kg total dose; the dose must be administered over a minimum period of at least 2 days, and may be administered over a period of up to 5 days).
- Adverse events.
- Concomitant therapies.
- Schedule next visit.

8.5.6.5 Retreatment Week 16 and Week 22 Visits

The following procedures will be conducted at the Retreatment Week 16 and Week 22 Visits:

- Urine or serum pregnancy test (for female subjects of childbearing potential).
- Blood draws:
 - Creatinine.

NOTE: The blood draw should be completed before administration of C1-INH and IVIg.

- Subcutaneous administration of blinded investigational product (C1-INH [60 IU/kg] or placebo, dose rounded to the lowest 1 mL).
- Investigational product dispense, if applicable.

- Investigational product vial return, if applicable.
- IVIg may begin if DSA is \geq 2000 MFI (2 grams/kg total dose; the dose must be administered over a minimum period of at least 2 days, and may be administered over a period of up to 5 days).
- Adverse events.
- Concomitant therapies.
- Schedule next visit.

8.5.6.6 Retreatment Week 26 Visit

The following procedures will be conducted at the Retreatment Week 26 Visit:

- Physical examination.
- Vital signs.
- Blood draws:
 - Creatinine.
 - Retention sample for viral serology.
 - Serum pregnancy test (for female subjects of childbearing potential).

NOTE: All blood draws should be completed before administration of C1-INH.

- Subcutaneous administration of blinded investigational product (C1-INH [60 IU/kg] or placebo, dose rounded to the lowest 1 mL).
- Investigational product vial return, if applicable.
- Adverse events.
- Concomitant therapies.
- Schedule next visit.

8.5.7 Non-responder Follow-up Period

The following will be collected during the Non-responder Follow-up Period at 3 months (\pm 2 days) following the Week 13 Visit, then every 6 months (\pm 28 days) until the end of the Non-responder Follow-up Period:

- Graft failure (yes/no, date of failure if available)
- Subject survival (yes/no)

- Development of biopsy-confirmed AMR (yes/no)
- Creatinine measurement

Creatinine will be measured by the central laboratory for prospectively collected samples from subjects who enter the Non-responder Follow-up Period after Amendment 3.

Creatinine values may be obtained retrospectively from medical records if samples cannot be drawn prospectively.

- EQ-5D-3L (Months 12, 24, 36, and 48)

8.5.8 Subject Withdrawal/Discontinuation

8.5.8.1 Withdrawal/Discontinuation during Treatment Period 1

If a subject is withdrawn/discontinued from the study for any reason during TP1, then the investigator should make every effort to perform the assessments scheduled for the Week 13 Visit. In addition, investigators should contact these subjects by telephone approximately 30 days after the Week 13 Visit (ie, End-of-TP1 Visit) to collect follow-up safety information.

8.5.8.2 Withdrawal/Discontinuation during Treatment Period 2

If a subject is withdrawn from the study for any reason during TP2, the investigator should make every effort to perform the assessments scheduled for the Week 38 Visit. In addition, investigators should contact these subjects by telephone approximately 30 days after the Week 38 Visit (ie, End-of-TP2 Visit) to collect follow-up safety information.

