- ^a If a subject is withdrawn from the study for any reason during Treatment Period 2, then the investigator should make every effort to perform the assessments scheduled for the Week 38 Visit. In addition, investigators should contact these subjects by telephone approximately 30 days after the Week 38 Visit (ie, the End of Treatment Period 2 Visit) to collect follow-up safety information.
- ^b A physical examination will be conducted per the investigator's standard procedure, and will also include assessment of unilateral pain and/or swelling of the lower extremities for the purpose of screening for deep vein thrombosis.
- ^c Vital signs assessments will include blood pressure, pulse rate, body temperature, and body weight.
- ^d Beginning during Treatment Period 2, a blood sample for creatinine measurement at the central laboratory [CL] will be drawn once every 14 days (\pm 7 days) at the study site or at home by a medical professional. Blood draws for creatinine measurements may occur more frequently at the investigator's discretion.
- ^e The biochemistry panel includes assessment of creatinine; the complete list of assessments included as a part of the biochemistry panel is presented in [Table 13](#).
- ^f Donor-specific antibodies will be measured in both the central and local laboratories. Central laboratory results will be used for analyses. Local laboratory results will be used by the investigator to make treatment decisions, including the initiation of IVIg and plasmapheresis. Additional blood draws for assessment of DSA will occur after plasmapheresis, as described in [Section 5.4.2](#).
- ^g A pregnancy test will be conducted for women of childbearing potential, only. Serum pregnancy test will be conducted at Week 16 and EoTP2. Urine or serum pregnancy tests will be conducted at all other timepoints.
- ^h A blood sample will be retained for potential future serology assessments.
- ⁱ Throughout Treatment Period 2, subcutaneous investigational product (C1-INH or placebo) will be administered as per the randomization schedule every 3 or 4 days (ie, twice weekly) at the study site, at home by a medical professional, or by the subject under the supervision of a medical professional. The first dose of randomized investigational product will be administered at the week 13 visit.

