8.5.8.4 Withdrawal/Discontinuation during the Follow-up Period

If a subject is withdrawn from the study for any reason during the Follow-up Period, the investigator should make every effort to perform the assessments scheduled for the Month 48 Visit.

9 Adverse Events

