6.7 CCI

CCI

7 General Considerations

Analysis datasets will be created according to CDISC standards, and data will be displayed according to reporting standards in this SAP and tables, figures and listings (TFL) formats.

SAS version 9.3 or higher will be used to perform all data analyses and to generate TFLs.

All ICH required data in the database will be presented in data listings.

Continuous variables will be summarized in terms of the number of observations, mean, standard deviation, median, Q1, Q3, minimum and maximum. Other descriptive statistics (eg, quartiles, coefficient of variation) may be reported when appropriate. Categorical variables will be summarized using frequency counts and percentages. Analyses that use other descriptive statistics will have the specific descriptive statistics required identified with the analysis in the applicable SAP section.

All listings will include subject number, treatment group. The laboratory normal reference ranges will be provided and clinical laboratory test results outside the normal reference range will be flagged in the laboratory data listings.

Summary statistics of central tendency will be reported to one more decimal place than the collected data. Summary statistics of variability will be reported to one more decimal place than the commensurate measure of central tendency. For example, the mean and median for age will be reported to one decimal place because it is collected in full years. The standard deviation of age will then be reported to 2 decimal places.

Formatting for dates and times will be: descriptive percentages and proportions will be displayed to one decimal place. Percentages and proportions to be tested will be calculated to 4 decimal places. Durations for events will be display to 1 decimal place.

- Dates only – ddmmmyyyy
- Times only – hh:mm or hh:mm.ss
- Dates and times – ddmmmyyyy hh:mm or ddmmmyyyy hh:mm:ss

In general, only scheduled visits will be included in by-visit summaries. However, worst-case or best-case values (as appropriate) will be derived using both scheduled and unscheduled visits. In general, assessment windows will not be defined for the purpose of classifying measurements obtained outside scheduled assessment times, other than those indicated in the Schedule of Assessments. However, exceptions may apply for creatinine / eGFR.

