8.2.7 Multiple Assessments

All data will be reported according to the nominal visit date/time for which it was assessed (that is, no visit windows will be applied during dataset creation).

If multiple assessments for the same visit occur, it will be distinguished why this is the case. If a laboratory sample was repeated due to technical problems the results from the valid sample(s) for this visit – the non-missing results – will be used in the analysis. If a laboratory sample was repeated as safety follow-up to monitor abnormal values of the initial sample, the initial sample (revealing the abnormal values) of this visit will be used in the analysis.

Data from all assessments (scheduled and unscheduled), including multiple assessments, will be included in listings.

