The mean of Week 36 and Week 38 eGFR measurements. If one of the measurements is missing it is then the non-missing value.

Response to Open-Label C1-INH at End of Treatment Period 1 (End-of-TP1)

Responders are defined as subjects whose End-of-TP1 (the mean of Week 11 and Week 12) eGFR $\geq 90\%$ of baseline and ≥ 20 mL/min/1.73 m². The baseline eGFR is defined as the mean of the screening and Day 1 values in [Section 8.2.5](#).

Loss of Response During Treatment Period 2

Loss-of-response at the End-of-TP2 is defined as any 1 of the following 3 conditions:

- End-of-TP2 eGFR (mean of Week 36 and Week 38 eGFR) that is not stable, defined as:
 - End-of-TP2 eGFR that is $< 90\%$ of the End-of-TP1 eGFR for subjects whose End-of-TP1 eGFR (mean of Week 11 and Week 12 eGFR) is $\geq 100\%$ of baseline;

- End-of-TP2 eGFR that is < 90% of baseline for subjects whose End-of-TP1 eGFR is ≥ 90% of baseline and < 100% of baseline.
- Allograft failure (defined by allograft nephrectomy, or institution of permanent dialysis, or return to the transplant waitlist for renal transplant, whichever occurs first)
- Subject death by any cause.

All-Cause Allograft Failure

All-cause allograft failure within 48 months after enrollment is defined as 1 of the following, whichever occurs first:

- Allograft failure (defined by allograft nephrectomy, or institution of permanent dialysis, or return to the transplant waitlist for renal transplant, whichever occurs first), OR
- Subject death by any cause.

No subject has reached 48 months after enrollment due to study termination.

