10.1 Analysis of Proportion of Subjects With Loss of Response at the End-of-TP2

The number and proportion of subjects with loss of response at the End-of-TP2 will be presented by treatment group along with the confidence interval for the difference between the two groups.

Subjects will be considered to have lost response if they drop-out or are lost to follow-up before the response status at the End-of-TP2 could be determined.

Components of loss-of-response at the End-of-TP2 will be summarized by treatment groups in terms of the proportion of subjects with:

- End-of-TP2 eGFR (mean of Week 36 and Week 38 eGFR values) that is not stable, defined as:
 - End-of-TP2 eGFR that is < 90% of the End-of-TP1 eGFR for subjects whose End-of-TP1 eGFR is \geq 100% of baseline,
 - End-of-TP2 eGFR that is < 90% of baseline for subjects whose End-of-TP1 eGFR is \geq 90% of baseline and < 100% of baseline,
- All-cause allograft failure (ie, allograft nephrectomy, or institution of permanent dialysis, or return to the transplant waitlist for renal transplant),
- Death by any cause.

The primary efficacy analysis will be conducted for the mITT Analysis Set.

10.1.1 Subgroup Analyses of Proportion of Subjects With Loss of Response at the End-of-TP2

The proportion of subjects with loss of response at the End-of-TP2 will be summarized by the treatment group for the following subgroups based on the following subgroup analyses outlined below will be conducted for the mITT Analysis Set.

The following subgroups, and possibly others to be described in the SAP, will be summarized by treatment group with respect to the proportion of loss-of-response:

- Geographic region: USA, non-USA,
- DSA by randomization strata: sensitized, de novo,
- DSA by classification: HLA class I, HLA class II, both HLA class I and II,
- AMR severity: severe, non-severe (all other severities),
- Type of donor: deceased, living,
- Recipient race: Black, non-Black,
- Recipient sex: Male, Female,
- Recipient age: < 65 years, \geq 65 years.

The difference in the proportion of response along with the 95% confidence interval will be also presented for each subgroup.

10.2 Analysis of key Secondary Endpoint Proportion of Subjects With All-Cause Allograft Failure Through the Responder Follow-up Period (ie, Within 48 Months After Enrollment)

No subject will complete the follow-up period of 48 months after enrollment. Therefore, this key secondary analyses cannot be conducted.

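### The SAP has two drop-out rules for TP2 response that disagree, and under one of them a creatinine drawn at early withdrawal could stand as the End-of-TP2 eGFR

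*Protocol*

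**What the plan says.** **Withdrawal in TP2.** Protocol 8.5.8.2 and footnote a of Protocol Table 2 ask for the Week 38 assessments when a subject is withdrawn from the study: "the investigator should make every effort to perform the assessments scheduled for the Week 38 Visit". The Week 38 list in Protocol 8.5.4.6 includes creatinine. Footnote a then times the safety call for these subjects "approximately 30 days after the Week 38 Visit (ie, the End of Treatment Period 2 Visit", so it refers to the withdrawal visit as Week 38. TP1 has its own early-withdrawal list (Protocol 8.5.3.14); TP2 has none.

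**Visit assignment.** SAP 8.2.7: "All data will be reported according to the nominal visit date/time for which it was assessed", with the addition that "no visit windows will be applied during dataset creation". SAP section 7 (General Considerations) refers to the windows in the Schedule of Assessments and says that "exceptions may apply for creatinine / eGFR", but defines no exception.

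**End-of-TP2 eGFR.** SAP 8.2.9: "The mean of Week 36 and Week 38 eGFR measurements. If one of the measurements is missing it is then the non-missing value".

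**Drop-out rule 1, SAP 8.1.1.** For percent responders in the ITT or mITT set, a subject who leaves the study after randomization, whenever that is, counts as a non-responder. There is no condition.

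**Drop-out rule 2, SAP 10.1 and Protocol 10.3.3.1.** Subjects are "considered to have lost response if they drop-out or are lost to follow-up before the response status" at End-of-TP2 could be determined. This rule is conditional.

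**The concern.** The primary endpoint is loss of response at Week 38, about 25 weeks after randomization. A subject who leaves the study early has no eGFR at that time. Both rules seem meant to count such a subject as a failure, but they do so differently, and each goes wrong in one place.

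Rule 2 depends on whether a status could be determined. If the withdrawal creatinine is filed under Week 38, the one-value rule yields an End-of-TP2 eGFR, a status exists, and a stable value counts as maintained response. Rule 1 prevents that, but taken literally it also fails a subject whose Week 38 status was properly determined and who left afterwards.

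At stake are the loss-of-response proportion in each arm and the confidence interval for their difference, which SAP 10.1 still reports.

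**Working it through.** **1. The rules side by side.** Three illustrative subjects, each with stable eGFR at the last sample:

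| Subject | SAP 8.1.1 | SAP 10.1 / Protocol 10.3.3.1 |
|---|---|---|
| A: leaves the study at Week 17 | Failure | Loss if the withdrawal sample is not used as Week 38; maintained if it is |
| B: stable at Weeks 36 and 38, leaves during follow-up | Failure, read literally | Maintained |
| C: stops product, stays in the study | Not a study drop-out; scored on true Week 36/38 values | Same |

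A and B can be scored differently under the two rules. C is unaffected, because Protocol 4.2.2 keeps such subjects on the assessment schedule.

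Timing for A: Week 38 is Day 38 × 7 = 266 and Week 17 is Day 17 × 7 = 119. The sample is 147 days (21 weeks) early, only 4 weeks after the Week 13 randomization. The largest possible gap is 38 − 13 = 25 weeks.

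**2. The plan's power figure, then sensitivity to the scoring rule.** Inputs from Protocol 10.1.1: loss 0.75 on placebo and 0.30 on C1-INH, 30 per arm, two-sided alpha 0.05, likelihood-ratio chi-square.

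- Mean proportion: (0.75 + 0.30)/2 = 0.525.
- Per-subject noncentrality: the sum over arms of p·ln(p/0.525) + (1−p)·ln((1−p)/0.475) = 0.1070 + 0.1036 = 0.2106.
- Total: 60 × 0.2106 = 12.64. Power = P(noncentral chi-square, 1 df > 3.84) = 94.5%.

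The stated figure of about 95% reproduces (the pooled two-proportion formula gives 95.7%).

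The documents give no TP2 drop-out rate, so the rates d below are assumptions. Completers keep 0.75 and 0.30. Expected loss is (1−d)·p + d if drop-outs count as loss, and (1−d)·p if all count as maintained.

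| Drop-out, placebo / C1-INH | Scored as loss: rates, power | Scored as maintained: rates, power |
|---|---|---|
| 10% / 10% | 0.775 vs 0.370, 89.7% | 0.675 vs 0.270, 89.0% |
| 20% / 20% | 0.800 vs 0.440, 83.1% | 0.600 vs 0.240, 81.6% |
| 10% / 20% | 0.775 vs 0.440, 76.7% | 0.675 vs 0.240, 93.1% |
| 20% / 10% | 0.800 vs 0.370, 93.1% | 0.600 vs 0.270, 74.0% |

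Equal drop-out hardly matters. A 10-point imbalance moves power by 16 to 19 points, either way. This describes the 60-subject design only.

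**3. The trial as it stands.** SAP section 3 gives 13 randomized. Assume arms of 7 (placebo) and 6 (C1-INH), all in the mITT set. One subject is 1/7 = 14.3 or 1/6 = 16.7 points; if the mITT set is smaller, the step is larger.

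With assumed counts, and Newcombe 95% intervals because SAP 10.1 names no method:

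- Placebo 5/7, C1-INH 2/6: difference −38 points (−69 to +13).
- One C1-INH loss re-scored as maintained (1/6): −55 points (−79 to −2).
- One placebo loss re-scored as maintained instead (4/7 vs 2/6): −24 points (−60 to +25).

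One subject's scoring can move the interval off zero or further across it.

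**The case against.** The best counter-argument is SAP 8.1.1. It is unconditional and names the randomized analysis sets, so under it a Week 17 withdrawal fails whatever creatinine was drawn. A reader might infer that the plan does score early drop-outs as maintained responders; the documents do not support that. Rule 2 read for its purpose also counts the Week 17 leaver as a loss. No text says that a withdrawal sample is stored as Week 38: the protocol says which assessments to perform, and the wording of the safety call only suggests the label. SAP section 7 also leaves room for creatinine windows. All of this stands, and it limits the point to an ambiguity.

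It does not remove the ambiguity. SAP 8.1.1 speaks of percent responders, whereas the loss-of-response endpoint has its own rule in SAP 10.1, and nothing ranks the two. SAP 8.1.1 is also hard to apply literally: no subject reached 48 months (SAP 8.2.9), and subject B would fail despite a valid Week 38 result. An analyst would have reason to fall back on SAP 10.1, where the route is open. The creatinine exception in section 7 is not defined.

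Two other inferences go too far. One is a definite bias toward no difference, or a large loss of power. That needs misclassified drop-outs in the placebo arm only; C1-INH drop-outs push the other way, and SAP 4.2.1.3 and 7.3 plan no formal testing. The other is that early leavers will be counted as surviving grafts at 48 months. Protocol 8.5.8.4 does say that "the investigator should make every effort to perform the assessments scheduled for the Month 48 Visit", and Protocol 10.3.3.2 gives no drop-out rule for that endpoint, but SAP section 5, 10.2 and 10.3 drop the analysis. That part is a protocol gap with no effect on the current report.

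**Conclusion.** The point holds as a conflict between two drop-out rules, together with a missing timing rule for the primary endpoint variable. It does not show that any subject has been or will be misclassified. For that to happen, the withdrawal sample must be filed as Week 38 and SAP 10.1 must be applied without SAP 8.1.1; the documents neither require nor exclude this.

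The effect falls on the descriptive proportions and their confidence interval, not on type I error. The 14 to 17 points per subject rest on the assumed arm sizes. The direction depends on which arm loses subjects, and the number affected is unknown. The correction is worth making because the endpoint is primary, the numbers are small, and the cost is slight.

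**What to change.** - **SAP 8.2.7 and 8.2.9:** label samples drawn at study withdrawal as Early Termination. Admit a creatinine to the End-of-TP2 mean, including under the one-value rule, only if its actual date is within 7 days of Week 36 (Day 36 × 7 = 252, so Days 245 to 259) or Week 38 (Day 266, so Days 259 to 273). Protocol Table 2 gives the 7 days for the Week 38 visit and for the fortnightly creatinine draws. Day 259 lies in both windows, so say to which it belongs. State that this is the creatinine exception left open in SAP section 7.
- **SAP 8.1.1 and 10.1:** state one rule in both places. Study withdrawal before the End-of-TP2 window is loss of response; withdrawal after a determined Week 38 status does not change it. Add that subjects who stop product but stay in the study keep their true Week 36 and Week 38 values.
- **Protocol 8.5.8.4 and 10.3.3.2, if the design is reused:** treat graft and survival status at withdrawal as last known status on that date, not as Month 48 status, unless it falls within the 28-day Month 48 window.

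The cost is a few sentences and one derivation flag. No new data are needed: the eGFR formula in SAP 8.2.9 already uses the actual sample date to compute age. Only one subject was still in TP2 at termination, so a new label would change little in data collection; the date rule does the work at analysis. The only downside is that a few subjects might move from stable to loss of response.
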